### **3.5.4 Analysis Populations**

#### **3.5.4.1 Efficacy Analysis Populations**

##### **Modified Intent-To-Treat (MITT) Population**

The key summaries and analyses for the primary, secondary and exploratory efficacy endpoints will be based on the MITT population (see Table 3-2). This population will include all randomized patients who received at least one dose of the vaccination. Those randomized patients who are excluded from the MITT population will be listed. The efficacy analyses will be performed based on the treatment group to which those subjects are randomized.

##### **Per Protocol Efficacy (PPE) Population**

Supportive analyses for the primary and key secondary endpoints will be conducted in the PPE population (see Table 3-2). This population will include those patients who received all 4 vaccination doses and did not present a case of HZ from Day 1 through 28 days post-dose 4.

To evaluate the risk of PHN or other complications, additional exploratory analyses will also be based on a subset of PPE population that developed HZ.

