### **3.5.3 Analysis Endpoints**

#### **3.5.3.1 Efficacy**

The primary efficacy endpoint is the incidence of confirmed HZ postvaccination in the vaccine and placebo groups in the STM population, defined as the number of HZ cases per 1000 person-years of follow-up (from study enrollment to the end of study). A supportive analysis will consider cases following 4 doses of vaccination based on the time period from the date of Dose 4 to the end of study. Final HZ case determination will be based primarily on the results of the skin lesion PCR. If the skin lesion PCR result is inadequate or missing, or if HZ presentation did not include a rash, case confirmation will be based on the results of case adjudication by the CAC.

Three secondary endpoints are defined for the STM population and in the HM population on an exploratory basis. The three secondary endpoints are defined as follows:

- (1) Each suspected case of HZ will undergo 6 months of follow-up for HZ-associated pain and HZ-associated complications. Moderate to severe HZ-associated pain [defined as 2 or more occurrences of scores 3 or greater (on a 0-to-10 scale)] will be assessed by the ZBPI questionnaire at any time from HZ onset through the end of the 6 month HZ-follow-up period. The response to the question, “Rate your worst pain in the last 24 hours on a 0-to-10 scale” from the ZBPI will be used for the aforementioned HZ pain analyses.
- (2) The HZ-associated complications endpoint is a composite endpoint that is defined as the proportion of patients experiencing at least one of the following HZ complications:
  - Hospitalization or prolongation of hospitalization due to HZ
  - Disseminated HZ (including disseminated HZ rash or VZV viremia)
  - Visceral HZ
  - Ophthalmic HZ
  - Neurologic impairment due to HZ
  - Intravenous acyclovir therapy for HZ

(3) The incidence of PHN in randomized patients is another secondary endpoint. PHN is defined as pain in the area of the HZ rash with a “worst pain in the last 24 hours” score of 3 or greater (on a 0 to 10 scale) on the ZBPI that persists or appears greater than or equal to 90 days after HZ rash onset. Sensitivity analyses on the comparison of the incidence of PHN persisting or appearing more than 30, 60, 120 and 182 days after HZ rash onset between the vaccination groups will also be performed.

Exploratory efficacy endpoints include:

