## **3.5.5 Statistical Methods**

### **3.5.5.1 Analysis of Vaccine Efficacy**

Table 3-2 summarizes the key efficacy analyses to be performed. The details are given in the following subsections.

Table 3-2

Summary of Key Efficacy Analyses Performed

Analysis	Method	Patient population
Primary		
HZ incidence - $VE_{HZ}$	Cox proportional hazards regression model with Efron's method of tie handling	MITT
Secondary		
(1) Incidence of moderate to severe HZ-associated pain	Cox proportional hazards regression model with Efron's method of tie handling	MITT
(2) A composite efficacy endpoint of the incidence of HZ complications during the study	Same as above	MITT
(3) Incidence of PHN	Same as above	MITT
Supportive		
HZ incidence - Vaccine efficacy	Cox proportional hazards regression model with Efron's method of tie handling	PP
Durability of efficacy	Kaplan-Meier method Piecewise exponential model	MITT MITT
Exploratory endpoints - Severity-by-duration of HZ pain Duration of pain Score-by-duration of ADLI Score-by-duration of general health status score (EuroQoL) Impact of HCU and Work and Productivity Loss HZ incidence	ANCOVA Summaries ANCOVA ANCOVA Poisson regression with generalized estimating equations Summaries by age categories and HM population	MITT

It should be noted that if a given patient develops two or more episodes of confirmed HZ, only the first episode will be used in the vaccine efficacy analyses. The patients with multiple episodes of HZ will be listed. Exploratory analysis of multiple episodes of HZ (such as the Wei, Lin and Weissfeld method [51]) may also be performed if a sizable proportion (e.g., >10%) of HZ patients develop multiple episodes.

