### 3.5.5.1.1 Analysis of Vaccine Efficacy on Incidence of HZ Cases

The primary efficacy endpoint is the incidence of HZ in the vaccine and placebo groups in the STM population, defined as the number of HZ cases per 1000 person-years of follow-up from study enrollment to the end of study. Vaccine efficacy for HZ ( $VE_{HZ}$ ) is defined as the relative reduction of the hazard rate of HZ in the V212 group compared with that in the placebo group in STM population. The primary statistical hypothesis for the primary efficacy is  $H_0: VE_{HZ} \leq 25\%$  versus  $H_1: VE_{HZ} > 25\%$ .

To address the primary hypothesis, a Cox proportional hazards regression model in VZV vaccine and placebo recipients stratified by age (< 50 years of age versus  $\geq 50$  years of age based on a MITT population as described in section 3.5.4.1) will be used as the primary analysis to compare the incidence of HZ between the vaccine and placebo groups. The study time period in the primary analysis will be from the enrollment to the stop date of HZ surveillance. Patients who do not develop HZ will be censored at the stop date of HZ surveillance. The follow-up time for patients who develop HZ will be from the enrollment to their HZ onset date. For the interim analysis, this stop date will be the corresponding database cutoff date for the analysis. Efron's method will be used to handle ties in event times.

A key supportive analysis will include calculation of  $VE_{HZ}$  using a PP population as described in section 3.5.4.1 based on Cox proportional hazards regression model. The study time period in the primary analysis will be from the date of Dose 4 to the stop date of HZ surveillance. The model and covariate adjustment will be similar to that noted in the MITT approach. In addition, incidence of HZ and  $VE_{HZ}$  will also be summarized by age group (50 to 59, 60 to 69, and 70+) as exploratory analyses.

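### Per-protocol follow-up starts at Dose 4 although the population is selected to be HZ-free for the next 28 days, so per-protocol incidence rates come out slightly too low

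*Combined protocol and SAP*

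**What the plan says.** Three places in the protocol's statistical section bear on this.

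- **Who is analysed.** Section 3.5.4.1 defines the per-protocol efficacy population as patients with all four doses who "did not present a case of HZ from Day 1 through 28 days post-dose 4".
- **When time runs.** Section 3.5.5.1.1 plans a key supportive estimate of vaccine efficacy "using a PP population as described in section 3.5.4.1 based on Cox proportional hazards regression model". It then says: "The study time period in the primary analysis will be from the date of Dose 4 to the stop date of HZ surveillance". The paragraph concerns the supportive analysis, so the reference to the primary analysis is a slip.
- **Which cases count.** Section 3.5.3.1 puts the primary endpoint on a rate scale, "defined as the number of HZ cases per 1000 person-years of follow-up", and gives the scope of the supportive work in these words: "consider cases following 4 doses of vaccination based on the time period from the date of Dose 4 to the end of study". It names no population there and mentions no 28-day exclusion.

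Table 3-2 lists HZ incidence and vaccine efficacy in the per-protocol set, with this method: "Cox proportional hazards regression model with Efron's method of tie handling". No passage delays entry to the risk set until after day 28.

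**The concern.** Patients are selected on being free of HZ over a period that is then counted as follow-up at risk. That period holds person-time but, by construction, no events, so any rate that uses it in the denominator is too low. A Kaplan-Meier curve for this population would open with 28 flat days that reflect the selection rule and not the disease.

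There is also a mismatch over cases. A patient with HZ on day 10 after Dose 4 falls inside the time window of 3.5.3.1 and 3.5.5.1.1 but is removed by 3.5.4.1. Section 3.5 says that no separate SAP will be issued, so this text is the only pre-specification of how such a patient is handled. At stake are the absolute per-protocol rates and a clear case rule for the supportive analysis. The primary test is not involved.

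**Working it through.** **1. Checks against the plan's own figures.** The documents give no numerical target for the per-protocol analysis, so these only confirm the inputs.

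- *Power (3.5.7.1):* 90 cases, null efficacy 25%, true efficacy 65%, one-sided 0.0125. Conditional on the total, a vaccine-arm case has probability 0.75/1.75 under the null and 0.35/1.35 under the alternative. The exact binomial rule is at most 27 vaccine cases of 90 (attained level 0.0083). Power is 84.2%, as stated.
- *Case accrual (3.5.7.1):* 1348 per arm, placebo rate λ = 0.017 per year (the plan's 17 per 1000, read as per person-year), vaccine rate 0.35 × 0.017 = 0.00595. I assume enrolment uniform over A = 3 years, study length T = 5 years, and the 30% loss spread exponentially over 5 years (η = −ln 0.7/5). With h = λ + η, expected cases per arm are n(λ/h)[1 − (e^(−h(T−A)) − e^(−hT))/(hA)]. This gives 68.4 placebo + 24.4 vaccine = 92.9, close to the planned 90, so the follow-up assumptions are reasonable.

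**2. Event-free time per patient.** 28/365.25 = 0.077 years. If all 1348 per arm qualified (an upper bound), that is 1348 × 0.077 = 103 person-years per arm and 207 in total.

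**3. Effect on a rate.** With mean follow-up m years from Dose 4, the rate as written is cases/m per patient. The rate over time actually at risk is cases/(m − 0.077). The proportional understatement is 0.077/m:

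| Mean follow-up after Dose 4 (years) | Understatement |
|---|---|
| 2.0 | 3.8% |
| 2.5 | 3.1% |
| 2.8 | 2.7% |
| 3.0 | 2.6% |

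The documents do not give m. The 2.8 years comes from the assumptions in step 1, with Dose 4 taken as 0.3 years after enrolment (administrative censoring 1.7 to 4.7 years after Dose 4). Larger values are hard to reach: with no loss at all, mean follow-up from enrolment is 5 − 3/2 = 3.5 years, and Dose 4 comes about 3 months later.

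**4. Simulation.** Exponential HZ times under these assumptions, with patients who had HZ in the first 28 days removed (40 data sets, five times the trial's size):

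| | Clock at Dose 4 | Clock after day 28 |
|---|---|---|
| Placebo, per 1000 person-years | 16.6 | 17.1 |
| Vaccine, per 1000 person-years | 6.03 | 6.20 |

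The understatement is 2.8% in the placebo arm and 2.7% in the vaccine arm. Efficacy from the rate ratio moves by less than 0.1 point. The Cox hazard ratios (Efron ties) agree to about 1e-15. This is expected: the partial likelihood is built only at event times, and no event falls in the first 28 days.

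**5. Cases in the ambiguous window.** Placebo: 1348 × 0.017 × 0.077 = 1.8. Vaccine: 1348 × 0.00595 × 0.077 = 0.6. The total is about 2.4 if every patient completes four doses, or 2.1 if 90% do (an assumption; 2.4 × 0.9).

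**The case against.** The strongest reply is that the sections answer different questions. Section 3.5.4.1 says who is analysed, and 3.5.5.1.1 says when time runs while adopting that population explicitly. A programmer can apply the filter and then start the clock at Dose 4. This stands. A reader might infer that the two sections cannot both be followed, but the documents do not support that. Section 3.5.3.1 is silent on the exclusion; it does not instruct anyone to keep the removed patients. The code would run, but with the event-free days left in the denominator.

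A reader might also infer that the supportive efficacy estimate hinges on which section is followed. That too goes beyond the documents. The clock does not alter the Cox estimate, and the roughly 2 ambiguous cases are expected to split 1.8 to 0.6, the same ratio as the assumed efficacy, so the expected shift is about nil. Chance could move it a little. With an illustrative 22:63 split and equal person-time, efficacy is 65.1%. Two more vaccine cases would make it 61.9%, and two more placebo cases 66.2%.

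Finally, the planned per-protocol method is a Cox model, and no passage clearly commits to a per-protocol rate table. The person-year summary by number of doses in 3.5.5.1.1 names the MITT population, and the Kaplan-Meier sentence there names none. This also stands, so the harm is conditional on such an output. It remains a likely one: the endpoint is defined per 1000 person-years and Table 3-2 lists HZ incidence for the per-protocol set.

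**Conclusion.** Wrong as written, but minor and confined to a supportive analysis. The per-protocol clock includes 28 days that the population definition guarantees to be free of cases. Any per-protocol rate would be about 2.7% too low in both arms if mean follow-up after Dose 4 is about 2.8 years. That mean rests on uniform enrolment over 36 months, a 5-year study, 30% loss spread over the 5 years, and Dose 4 about 0.3 years after enrolment. Neither the per-protocol Cox efficacy nor the primary MITT analysis and its success criterion is affected by the clock. The wording of 3.5.3.1 adds an ambiguity over about 2 expected cases, with little expected effect on efficacy.

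**What to change.** Make three small edits before unblinding:

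1. In 3.5.5.1.1, start per-protocol time on day 29 after Dose 4, for patients still at risk on that day. Patients censored earlier then contribute no time.
2. In 3.5.3.1, state the same start and name the per-protocol population.
3. In the sentence of 3.5.5.1.1 that gives the Dose 4 start, replace the reference to the primary analysis with one to this supportive analysis.

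Keeping the Dose 4 clock and excluding only HZ before Dose 4 would also be coherent, and would fit the present wording of 3.5.3.1. The day-29 start is preferable because it leaves the population definition in 3.5.4.1 as it is.

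The cost is a few phrases. No new data are needed and no primary test changes. Reported per-protocol rates rise slightly.

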### **3.5.4.2 Immunogenicity Analysis Populations**

#### **Per Protocol Immunogenicity (PPI) Populations**

The immunogenicity summaries and analyses will be provided for the PPI population. To be included in this population, patients must:

- (1) Have received all 4 vaccination doses
- (2) Have not reported any exposure to varicella/HZ within 4 weeks prior to blood draw
- (3) Have not develop any suspected varicella/HZ before the relevant blood sampling
- (4) Have not received medical treatments (such as blood products, immunoglobulin therapy) that may interfere with one or both of the proposed immunogenicity measurements.

Based on criterion (4), some patients may be excluded from only one of the 2 immunogenicity analysis (gpELISA, ELISPOT). The final determination of patients excluded from one or both immunogenicity analyses, and thereby the composition of the Per Protocol immunogenicity analysis populations, will be made prior to the final unblinding of the database and will be documented in a separate memo.

### **3.5.4.3 Safety Analysis Populations**

All patients who receive at least 1 dose of vaccine/placebo and have follow-up data will be included in the safety and tolerability summaries and analyses. The safety analyses will be based on the All Subjects as Treated (ASaT) approach.

## **3.5.5 Statistical Methods**

### **3.5.5.1 Analysis of Vaccine Efficacy**

Table 3-2 summarizes the key efficacy analyses to be performed. The details are given in the following subsections.

Table 3-2

Summary of Key Efficacy Analyses Performed

Analysis	Method	Patient population
Primary		
HZ incidence - $VE_{HZ}$	Cox proportional hazards regression model with Efron's method of tie handling	MITT
Secondary		
(1) Incidence of moderate to severe HZ-associated pain	Cox proportional hazards regression model with Efron's method of tie handling	MITT
(2) A composite efficacy endpoint of the incidence of HZ complications during the study	Same as above	MITT
(3) Incidence of PHN	Same as above	MITT
Supportive		
HZ incidence - Vaccine efficacy	Cox proportional hazards regression model with Efron's method of tie handling	PP
Durability of efficacy	Kaplan-Meier method Piecewise exponential model	MITT MITT
Exploratory endpoints - Severity-by-duration of HZ pain Duration of pain Score-by-duration of ADLI Score-by-duration of general health status score (EuroQoL) Impact of HCU and Work and Productivity Loss HZ incidence	ANCOVA Summaries ANCOVA ANCOVA Poisson regression with generalized estimating equations Summaries by age categories and HM population	MITT

It should be noted that if a given patient develops two or more episodes of confirmed HZ, only the first episode will be used in the vaccine efficacy analyses. The patients with multiple episodes of HZ will be listed. Exploratory analysis of multiple episodes of HZ (such as the Wei, Lin and Weissfeld method [51]) may also be performed if a sizable proportion (e.g., >10%) of HZ patients develop multiple episodes.

### 3.5.5.1.1 Analysis of Vaccine Efficacy on Incidence of HZ Cases

The primary efficacy endpoint is the incidence of HZ in the vaccine and placebo groups in the STM population, defined as the number of HZ cases per 1000 person-years of follow-up from study enrollment to the end of study. Vaccine efficacy for HZ ( $VE_{HZ}$ ) is defined as the relative reduction of the hazard rate of HZ in the V212 group compared with that in the placebo group in STM population. The primary statistical hypothesis for the primary efficacy is  $H_0: VE_{HZ} \leq 25\%$  versus  $H_1: VE_{HZ} > 25\%$ .

To address the primary hypothesis, a Cox proportional hazards regression model in VZV vaccine and placebo recipients stratified by age (< 50 years of age versus  $\geq 50$  years of age based on a MITT population as described in section 3.5.4.1) will be used as the primary analysis to compare the incidence of HZ between the vaccine and placebo groups. The study time period in the primary analysis will be from the enrollment to the stop date of HZ surveillance. Patients who do not develop HZ will be censored at the stop date of HZ surveillance. The follow-up time for patients who develop HZ will be from the enrollment to their HZ onset date. For the interim analysis, this stop date will be the corresponding database cutoff date for the analysis. Efron's method will be used to handle ties in event times.

A key supportive analysis will include calculation of  $VE_{HZ}$  using a PP population as described in section 3.5.4.1 based on Cox proportional hazards regression model. The study time period in the primary analysis will be from the date of Dose 4 to the stop date of HZ surveillance. The model and covariate adjustment will be similar to that noted in the MITT approach. In addition, incidence of HZ and  $VE_{HZ}$  will also be summarized by age group (50 to 59, 60 to 69, and 70+) as exploratory analyses.

The results of HZ case determination (PCR versus case adjudication by the CAC) will be summarized by vaccination group. The probability of developing HZ will be estimated and displayed by the Kaplan-Meier method. The incidence rates of HZ post randomization (enrollment) in each group will be compared by the nonparametric log-rank statistic without covariate adjustment. Also, the incidence of HZ will be summarized by vaccination group in terms of number of cases per 1000 person-years in those patients who only received a total of 1 dose, 2 doses, and 3 doses of vaccine/placebo using the MITT population if a sizable proportion (>10%) is observed in each category (1 dose, 2 doses, and 3 doses).

